Observational Study Participants: The study will include men and women aged 45–64 who are residents of Kaunas City and live in private apartments. Approximately 1,000 individuals will be randomly selected. Individuals living in institutions, rented accommodations, or nursing homes will be excluded from the study.

Experimental Clinical Trial Participants – Inclusion Criteria: Participants must be aged 45–64, male or female, residents of Kaunas City, and randomly selected from the observational study cohort. They must agree to wear a smart wristband sensor for 7 days and sign an informed consent form to participate in the healthy lifestyle intervention. A total of 180 participants will be enrolled.

Exclusion Criteria for Clinical Trial: Participants will be excluded if they have unstable angina, cardiomyopathy, hypertension with blood pressure greater than 160/110 mmHg, cardiac pacemakers, neurological diseases, alcohol dependence, limited mobility, or if they are pregnant.

Justification for Sample Size: The experimental clinical trial involving 180 participants will be conducted by researchers at VMU. The trial will assess the impact of a healthy lifestyle on early metabolic responses (biomarkers and health risks), considering individual PM0.1 exposure levels. To enhance data reliability and reducing the risk of Type I error (false positive) the confidence level is set up at 99.9%. The sample size was calculated using the formula:

$$N=2\times(Z_{1-\alpha/2}+Z_{1-\beta}/\delta_0)^2 \times p \times (1-p),$$

Where:

- N = required sample size
- $Z_{1-\alpha/2} = 3.29$ (for a 0.1% significance level)
- $Z_{1-\beta} = 0.842$ (for 80% statistical power)
- $\delta_0 = \text{effect size} = 0.1$
- $p = \text{expected proportion} = 0.3$

This gives:

$$N \approx 2 \times (3.29 + 0.842 / 0.1)^2 \times 0.3 \times 0.7 \approx 58 \text{ participants}$$

To account for potential dropouts (e.g., due to acute infections), a sample size of 60 per group is proposed. Therefore, a total of 180 participants will be enrolled in the clinical trial.

8. Biomedical Research Methodology

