Each group's clinical health indices and metabolic responses will be assessed by measurements blood pressure, waist circumference, high-density lipoproteins (HDL), triglycerides, plasma glucose levels, also metabolomic, proteomic, and DNA methylation biomarkers before and after the 7-day intervention. Primary proteomics screening comprises of 4–6 oxidative stress and inflammation markers via immunoblotting. In a second phase, based on the initial results, advanced OMICs analysis will be conducted using high-resolution techniques, such as redox/phospho-proteomics, metabolomics, DNA methylation via EPIC chip (for genome-wide methylation analysis). All data will be analysed using mathematical modelling to account for confounding variables. Results will substantiate recommendations for reducing metabolic disorder risks, targeted to healthcare professionals and the public.

Data Analysis and Evaluation: Both the observational and experimental clinical studies will use a standardized exposure–health response analysis approach. Key methods: multivariate logistic regression analysis, adjustment for confounding factors using mathematical modelling to estimate the strengths of the relationship and 95% confidence intervals between the variables.

Biological samples for metabolic response analysis will be sent to accredited partner laboratories:

- DNA methylation analysis: National Center of Pathology (Lithuania), Laboratoire National de Santé (Luxembourg)
- Proteomic analysis: University of Southern Denmark (Odense, Denmark)

- Metabolomic analysis: Institute for Molecular Sciences, University of Eastern Finland (Finland)

9. Description of Study Sites and Institutions Involved in Biomedical Research Activities

The METSGREEN biomedical research is being conducted together with 15 international scientific MARKOPOLY project centres, as part of an international collaboration. The participating institutions are:

1. Universitätsmedizin der Johannes Gutenberg-Universität Mainz (Germany) – *Coordinator*
2. Università degli Studi di Padova (Italy)
3. Medical University of South Carolina (United States)
4. Vytautas Magnus University (Lithuania)
5. University of Belgrade, Faculty of Medicine (Serbia)
6. The Cyprus Institute (Cyprus)
7. Concentris research management gmbh (Germany)
8. Max Planck Society for the Advancement of Science (Germany)
9. Laboratoire National de Santé (Luxembourg)
10. Luxembourg Institute of Health (LIH) (Luxembourg)

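### The Section 7 sample-size formula divides only Z(1-beta) by the effect size, so the stated 80% power does not hold for 60 per group; the protocol should also say which confidence level judges the trial contrasts

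*Protocol*

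**What the plan says.** Protocol Section 7, under the sample-size justification, sets the level for the trial: "To enhance data reliability and reducing the risk of Type I error (false positive) the confidence level is set up at 99.9" per cent. The listed inputs are Z(1-alpha/2) = 3.29 ("for a 0.1% significance level"), Z(1-beta) = 0.842 ("for 80% statistical power"), an effect size of 0.1 and an expected proportion of 0.3. In the symbolic formula the effect size divides Z(1-beta) alone. The worked line has the same form, "3.29 + 0.842 / 0.1)^2", and gives 58. This is raised to 60 per group for dropouts, hence 180 in three groups.

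Section 8, under data analysis and evaluation, says: "Both the observational and experimental clinical studies will use a standardized exposure–health response analysis approach". The methods named are "multivariate logistic regression analysis" and adjustment for confounders, "to estimate the strengths of the relationship and 95% confidence intervals between the variables". The same section says of the trial: "Results will substantiate recommendations for reducing metabolic disorder risks, targeted to healthcare professionals and the public".

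**The concern.** The usual formula for comparing two proportions divides the sum of both Z values by the difference to be detected. Dividing only one of them leaves 3.29 unscaled beside 0.842/0.1 = 8.42, so the significance level adds far too little to the sample size. This is the only numerical basis the protocol gives for 180 participants. If 80% power is taken at face value, an inconclusive comparison could be read as evidence that walking in green space or the diet has no effect. The trial indicators are secondary endpoints, but the results are meant to support recommendations to professionals and the public.

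A smaller question follows. Correct power depends on the level at which results are judged. Section 7 gives 99.9% and Section 8 gives 95%, and no sentence connects them.

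**Working it through.** **Inputs** (Section 7): Z(1-alpha/2) = 3.29; Z(1-beta) = 0.842; effect size 0.1; p = 0.3, so p(1-p) = 0.21; 60 per group. For a 5% level, Z(1-alpha/2) = 1.96. Assumption: 0.1 is an absolute difference in proportions. The protocol calls it only an effect size, but the p(1-p) factor implies this reading.

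**1. The protocol's figure reproduced.** 2 × (3.29 + 0.842/0.1)² × 0.21 = 2 × 11.71² × 0.21 = 57.6, rounded up to 58. The result depends on the misplaced division. Standard two-proportion forms (one- or two-sided, with or without continuity correction), a one-sample form and a standardised-effect form do not give about 58. The symbolic and worked lines agree with each other, so this is not an artefact of reading the PDF.

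**2. Correct form, same inputs.** N per group = 2 × ((Z(1-alpha/2) + Z(1-beta))/0.1)² × p(1-p).
- At 0.1%: 2 × (4.132/0.1)² × 0.21 = 717.1 per group.
- At 5%: 2 × (2.802/0.1)² × 0.21 = 329.8 per group.

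These are about 12 times and 5.5 times the planned 60 (717.1/60 and 329.8/60).

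**3. Power of 60 per group for a difference of 0.1.** Power ≈ Φ(0.1/SE − Z(1-alpha/2)).

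| Variance used | SE | 0.1/SE | Power at 0.1% | Power at 5% |
|---|---|---|---|---|
| Formula's own: √(0.42/60) | 0.0837 | 1.195 | 1.8% | 22.2% |
| 0.3 v 0.2: √((0.21 + 0.16)/60) | 0.0785 | 1.273 | 2.2% | 24.6% |
| 0.3 v 0.4: √((0.21 + 0.24)/60) | 0.0866 | 1.155 | 1.6% | 21.0% |

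Power is therefore about 2% at 0.1% and about 21-25% at 5%. A simulated Wald test on the log odds ratio, closer to the planned logistic regression, gave about 1% and 20-22%.

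**4. Difference detectable with 80% power at 60 per group**, using the formula's variance: (Z(1-alpha/2) + 0.842) × √(0.42/60).
- At 0.1%: 4.132 × 0.0837 = 0.346, about 0.35.
- At 5%: 2.802 × 0.0837 = 0.234, about 0.23.

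**5. Does another reading rescue 80%?** One-sided testing gives 2.5-3.3% at 0.1% and 31-35% at 5%. Taking 0.1 as a standardised effect removes the factor 0.21 and needs more: 2 × (4.132/0.1)² = 3,415 or 2 × (2.802/0.1)² = 1,570 per group. Neither reading rescues it.

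**6. Why the level needs stating.** As an illustration with invented counts, compare 8/60 with 18/60, unadjusted. The odds ratio is (8/52)/(18/42) = 0.36, and the SE of its logarithm is √(1/8 + 1/52 + 1/18 + 1/42) = 0.473. The 95% interval is 0.14 to 0.91 and the 99.9% interval is 0.08 to 1.70. If intervals are used to judge effects, the conclusion depends on the level chosen.

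**The case against.** The arithmetic of the formula has no good defence. There are three fair objections to making more of this.

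**The two levels need not conflict.** A reader might infer that 99.9% in Section 7 and 95% in Section 8 contradict each other. The 99.9% stands within the sample-size justification and is then used only as the input Z = 3.29. The 95% intervals are for estimation, and Section 8 states no test rule. A strict design level and conventional reporting intervals can coexist, so a contradiction is not shown. What remains is narrower. The stated reason for 99.9% is to reduce Type I error, and that is achieved only if 0.1% is also used to judge the results. Section 8 covers the trial by name, and nothing says which level decides.

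**The power figures have limited reach.** A reader might infer that the trial has only 2% or 21-25% power for its clinical indicators. The protocol does not support this. Waist circumference, blood pressure, HDL, triglycerides, glucose and the omics markers are measured before and after the intervention, and the protocol does not say what p = 0.3 is a proportion of. The figures show that the printed claim fails on its own terms and no more.

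**The shortfall does not mean the trial must grow.** A reader might infer that about 717 or 330 per group must be enrolled. Those numbers follow only if a 0.1 difference in this undefined proportion must be detected with 80% power. The trial serves secondary objectives, and 60 per group may be retained if its capability is stated correctly.

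**Conclusion.** The formula defect is established, and the stated 80% power is wrong at either level, in either direction of effect, and for one- or two-sided testing. The conclusion rests on a normal approximation, p = 0.3 and 0.1 as an absolute difference; the standardised reading only widens the gap. It concerns the assumed binary outcome, not the continuous indicators. It should be corrected before the data are analysed.

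The unstated decision level is a minor clarification, not a demonstrated contradiction. It concerns the trial only; the observational study is not affected. It belongs with this point because the restated power must be tied to one level.

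**What to change.** In Section 7, replace the formula with N per group = 2 × ((Z(1-alpha/2) + Z(1-beta))/delta)² × p(1-p) and correct the worked line. Say that delta is an absolute difference and which outcome p = 0.3 describes. Keep 60 per group, and replace the 80% claim with one of these:
- the power for a 0.1 difference (about 2% at 0.1%, about 21-25% at 5%); or
- the difference detectable with 80% power (about 0.35 at 0.1%, about 0.23 at 5%, using the formula's variance).

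State which level judges the trial contrasts. Either use one level in both sections, or name 0.1% as the decision level and label the 95% intervals descriptive. Base the restated power on that level.

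The cost is one recalculation and text edits to Sections 7 and 8, with no change to enrolment or procedures. The price is a much less favourable stated power for 180 participants. Choosing 5% would also give up the stricter Type I control that Section 7 claims.

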Measures to Reduce Subjective Bias: Participants will be randomly assigned to the three clinical trial groups. Only individuals without the listed health exclusions and who sign informed consent will be included. Assignment to the one of three groups will follow a 1:1:1 ratio. The researcher will handle group allocation and coding. Objective environmental pollution measurements and individual residential exposure will be taken. Seven-day monitoring health outcomes include physical activity, sleep disturbances, heart function. Two health checks will include measurements of blood pressure, body composition, waist circumference, body mass index (BMI) and biomarkers. Blood samples (up to 20 ml) will be collected to analyse metabolic biomarkers.

Mathematical modelling will be used during data analysis. It will control for confounding factors to assess the strength of the exposure–health outcome relationship.

Biomedical Study Plan: The study plan and phases are shown in Figure 1.

Observational Study: A representative sample survey of Kaunas residents will be conducted by a certified survey company that complies with strict personal data security, privacy principles, and legal requirements. In accordance with the General Data Protection Regulation (GDPR), data will be securely stored, lawfully processed, and participants will be able to exercise their rights easily. The internet survey will be conducted using the Google Forms platform, which provides data encryption and access control (limited to authorized personnel). Google services comply with EU data protection regulations, including two-factor authentication, ensuring the confidentiality and security of personal data. Approximately 1,000 individuals aged 45–64 will be included based on their responses to an anonymous online survey, which collects self-reported health indicators (physician-diagnosed chronic diseases), socioeconomic status, and basic residential information.

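### The sample-size formula divides only one of its two Z values by the effect size: it gives 58 per group where the protocol's own inputs require about 717, and 60 per group has about 2% power, not 80%, for the stated difference.

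*Protocol*

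**What the plan says.** The justification for sample size in Protocol Section 7 covers the randomised lifestyle trial. It says "the confidence level is set up at 99.9" per cent and takes Z(1-α/2) = 3.29 ("for a 0.1% significance level") and Z(1-β) = 0.842 ("for 80% statistical power"). The effect size δ0 is 0.1 and the expected proportion p is 0.3.

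The symbolic formula adds Z(1-α/2) to the quotient Z(1-β)/δ0, squares the sum, and multiplies by 2p(1-p). The worked line repeats that structure with the bracket "3.29 + 0.842 / 0.1)^2" and arrives at about 58 participants. After an allowance for dropouts, "a sample size of 60 per group is proposed. Therefore, a total of 180 participants will be enrolled in the clinical trial". Section 8 confirms the three-arm design: "Assignment to the one of three groups will follow a 1:1:1 ratio".

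**The concern.** In the usual formula for comparing two proportions, the detectable difference divides the whole sum Z(1-α/2) + Z(1-β). Here it divides only the second term. When δ0 is well below 1, leaving the first term undivided makes the answer far too small.

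This calculation is the only basis given for the size of the trial. If it is wrong, the stated 80% power does not exist, and the reader does not know what 180 participants can show. That matters because Section 8 says the results will support recommendations to healthcare professionals and the public. A non-significant comparison reported beside a claim of 80% power could be taken as evidence against an effect the trial had little chance of detecting.

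**Working it through.** **Inputs, all from Protocol Section 7 (Justification for Sample Size):** Z(1-α/2) = 3.29 (two-sided α = 0.001); Z(1-β) = 0.842 (80% power); δ0 = 0.1; p = 0.3, so p(1-p) = 0.21; 60 per group planned.

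**1. Reproducing the protocol's figure.** As printed:

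N = 2 × (3.29 + 0.842/0.1)² × 0.21 = 2 × (3.29 + 8.42)² × 0.21 = 0.42 × 11.71² = 57.6, reported as 58.

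The misplaced division was therefore carried out. It is not a bracket lost in typesetting. Standard alternatives at the same α, power and difference do not give 58: two-sided two-sample versions give 639 to 796 (the highest with continuity correction), one-sided versions 579 to 722, and a one-sample version 359.

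**2. Is the printed form a valid alternative?** Set power to 50%, so that Z(1-β) = 0. The printed formula becomes 2 × 3.29² × 0.21 = 4.5 per group for every effect size, however small. No valid sample-size formula behaves in this way.

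**3. Correct form, same inputs.**

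n per group = 2 × ((3.29 + 0.842)/0.1)² × 0.21 = 0.42 × 41.32² = 717.1

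This is 717 per group, or 718 rounded up, and 2,151 to 2,154 over three groups. Against the plan: 717/60 ≈ 12.

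**4. Power of 60 per group for a difference of 0.1.**

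SE = √(2 × 0.21/60) = 0.0837, so δ0/SE = 1.195.

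- Two-sided α = 0.001: Φ(1.195 − 3.29) = Φ(−2.095) = 1.8%
- Two-sided α = 0.05: Φ(1.195 − 1.96) = Φ(−0.765) = 22%

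At α = 0.05, 80% power would need 2 × ((1.96 + 0.842)/0.1)² × 0.21 ≈ 330 per group.

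**5. Difference detectable with 80% power.**

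| Evaluable per group | SE | α = 0.001 | α = 0.05 |
|---|---|---|---|
| 60 | 0.0837 | 0.0837 × 4.132 = 0.346 | 0.0837 × 2.802 = 0.234 |
| 58 | 0.0851 | 0.0851 × 4.132 = 0.352 | 0.0851 × 2.802 = 0.238 |

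**6. Sensitivity to where the proportions lie (two-sided α = 0.001, no continuity correction).**

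| Proportions | n per group for 80% power | Power at 60 per group |
|---|---|---|
| 0.30 v 0.40 | 776 | 1.6% |
| 0.25 v 0.35 | 716 | 1.8% |
| 0.30 v 0.20 | 639 | 2.1% |

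The conclusion does not depend on this choice.

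**7. What 60 per group gives for a continuous outcome.** At two-sided 0.05 with 80% power, an unadjusted two-sample t-test detects 0.516 SD. If the Day 1 value is a covariate with correlation r to the Day 8 value, this is multiplied by √(1 − r²). The protocol gives no r. Over an assumed range: r = 0.3, 0.49 SD; r = 0.5, 0.45 SD; r = 0.7, 0.37 SD; r = 0.9, 0.23 SD.

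**The case against.** The arithmetic itself is hard to contest, so the best counter-case concerns its reach.

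- **The 2% depends on α = 0.001, while Section 8 plans 95% confidence intervals.** This is fair, and both figures should be given. At 5% the power is 22%, still far from 80%.
- **δ0 is labelled only as an effect size, and no binary endpoint is named.** Reading it as an absolute difference in proportions is an inference. It is the only reading that fits the p(1-p) variance term.
- **N might be a total.** The protocol itself goes from 58 to 60 per group. If 58 were a total, the shortfall would be larger.
- **The trial's outcomes are mostly continuous, with measurements before and after the intervention.** This stands as a limit: the 2% describes the comparison the protocol sized for, not blood pressure, waist circumference or the biomarkers. Power for those cannot be derived from the stated inputs. That does not rescue the 80% claim. It means the only justification given for 180 participants fails and nothing replaces it.
- **The trial serves secondary objectives.** True, but it remains a randomised three-arm study with a stated power that is incorrect.

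**Conclusion.** The concern holds. The effect size is applied to one Z value instead of to the sum of both, in the symbolic formula and in the worked line, and nothing elsewhere in the protocol corrects it. The 58, the 60 per group and the total of 180 all follow from this error.

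On the protocol's own inputs the requirement is 717 per group, about 12 times the plan. The planned groups have 1.8% power at two-sided 0.001 (1.6% to 2.1% across plausible placements of the proportions) and 22% at two-sided 0.05. These figures assume that δ0 is an absolute difference between two proportions, that N is per group, and that one pairwise comparison is made. They do not show that 180 participants are too few for a continuous endpoint, only that the stated justification does not support the number. Because the claim of 80% power is false as written, it must be corrected.

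**What to change.** In the sample-size paragraph of Section 7:

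1. Write the formula with δ0 dividing the sum of both Z values, and remove the result of 58.
2. Withdraw the claim of 80% power for a difference of 0.1 at the 0.1% level.
3. Keep 180 participants and state what 60 per group can detect, at a significance level consistent with the 95% intervals in Section 8 or with the difference explained.
   - *Preferred:* base this on one named continuous endpoint, such as change in systolic blood pressure or in waist circumference. At two-sided 5% with 80% power, 60 per group detects about 0.52 SD unadjusted. With the Day 1 value as covariate and an assumed correlation of 0.7 it is about 0.37 SD. The correlation should be justified or shown as a range.
   - *If a proportion is kept:* name the binary endpoint and give the detectable difference as about 23 percentage points at 5%, or about 35 at 0.1%.
4. Say whether the figure applies to each intervention arm against control, and give the detectable effect for the number expected to be evaluable after dropout.

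The cost is a rewritten paragraph. No participants, visits or procedures are added. The stated sensitivity of the trial becomes less favourable, but correct.

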Measured concentrations of PM0.1 and noise levels in 20 locations across the city of Kaunas. Using a land-use regression (LUR) model, exposure levels for 1,000 participants will be modelled and linked to self-reported health outcomes: prevalence of CVD, blood pressure, waist circumference, and anthropometric data.

Secondary Endpoints:

During the experimental clinical trial (7-day healthy lifestyle intervention), involving 180 participants, key indicators of metabolic disorders will be assessed, including waist circumference and blood pressure measurements, high-density lipoprotein (HDL) levels, triglycerides, plasma glucose concentration, as well as biological markers from metabolomics, proteomics, and DNA methylation. These will be analyzed in relation to environmental exposure, socioeconomic status, and healthy lifestyle factors. Recommendations will be developed for reducing the risk of metabolic disorders.

6. Justification for the Biomedical Research

The international research's "Noise and/or ultrafine particulate matter induced cerebral and cardiovascular damage: novel insights from experimental and epidemiological studies and computational models" (MARKOPOLY) part conducted at Vytautas Magnus University (VMU), title: "Ambient air and noise pollution effect on cardiovascular health risk and lifestyle intervention to attenuate it in 45–64-year population" (METSGREEN), is being conducted to the order of the European Commission, which provides the necessary funding for its implementation. The MARKOPOLY is coordinated by Johannes Gutenberg University in Germany.

Environmental exposures increase health risk factors and account for up to two-thirds of all chronic non-communicable diseases¹. Environmental-related risk factors, among them air pollution, and personal lifestyle habits can contribute to the increase the global burden of CVD such metabolic syndrome, arterial hypertension, and diabetes mellitus. In Europe, approximately 500,000 premature deaths occur annually due to air pollution. However, particulate matter and noise thresholds are not currently incorporated into clinical guidelines. Moreover, the official European environmental pollution limits significantly exceed the standards set by the World Health Organization (WHO). This issue is especially critical for the most vulnerable populations—those affected by social exclusion, chronic illnesses, or advanced age.

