Experimental Clinical Trial: Participants who completed the online survey and conform to the study inclusion criteria will be eligible. Those interested in participating in the healthy lifestyle clinical trial can contact the researchers via the details provided in the internet survey form. Upon contact, participants will be asked to updated information on waist circumference, blood pressure, and address. Eligible participants will be invited to the Family Medicine Clinic of Kaunas Clinics at the Lithuanian University of Health Sciences (LSMU).

Inclusion criteria: Age 45–64, residence in Kaunas City on streets with identified high air pollution levels, and self-reported metabolic disorder indicators such as increased waist circumference and/or elevated blood pressure. Following contact, appointment times will be coordinated. At the initial visit, researchers will review the participant's health status. Participants will be informed about the experimental clinical trial and will sign an informed consent form. They will then be randomly assigned to one of three healthy lifestyle groups and instructed on their 7-day health behaviour study. Groups: 1. Control group (usual routine); 2. Physical activity in green space (daily 30-minute brisk walk); 3. Mediterranean diet intervention.

All groups' participants health assessments will be conducted by family doctor on Day 1 and Day 8 using certified medical equipment. Participants will be asked to arrive fasting or having not eaten for at least 2 hours before their visit.

Procedures will include:

- Blood sampling (up to 20 ml) for analysis of metabolic biomarkers
- Blood pressure measurement
- Waist circumference measurement
- Body composition analysis

All participants will wear Fitbit Alta wristband sensors for 7 days, which will collect digital data on physical activity (METs), step count, heart rate, sleep quality. Collected data will be transferred to a secure digital platform and coded to assess the results.

[figure not shown]

Fig. 1 Scheme of the Kaunas Clinical study

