An anonymous online questionnaire will be used for the survey. At the end of the questionnaire, information will be provided about the planned clinical trial, including details about the study process and contact information for the research team. Individuals who are interested in participating in the healthy lifestyle clinical trial will be able to reach out to the researchers directly. Upon initial contact, the research team will request clarification on several indicators, including the participant's waist circumference, blood pressure, and residential address. If the individual meets the inclusion criteria, the research team will invite them to participate in the clinical trial.

Inclusion criteria for the clinical trial:

- Age between 45 and 64 years
- Residence in Kaunas City, specifically in areas with documented high levels of air pollution
- Reported health data indicating signs of metabolic disorders, such as increased waist circumference and/or elevated blood pressure.

14. Procedure and Specifics of Informing About the Biomedical Research and Obtaining Informed Consent

When a respondent contacts the research team and expresses interest to participate in the healthy lifestyle clinical trial, the researcher will verify whether the individual meets the inclusion criteria. If eligible, the respondent will be provided with detailed information about the study and asked to share contact information for further communication. An appointment will then be arranged at the Family Medicine Clinic of Kaunas Clinics. Participants will be asked to arrive having fasted for at least two hours, as a blood sample (up to 20 ml) will be collected from a vein at the start of the clinical study.

During the first visit, the participant will be thoroughly informed about:

- The purpose and design of the biomedical research
- The methods applied in the study

- The decisions of the ethics committee
- The potential benefits of participation
- The participant's rights
- Possible risks and inconveniences
- The right to withdraw written consent to participate at any time
- The consequences of withdrawing from the study
- Confidentiality and data protection assurances.

After reviewing this information, the participant will be asked to sign the Informed Consent Form. The participant will also be reminded that a second blood sample will be collected after 8 days. For this second collection, fasting for at least two hours will again be required.

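### The two-hour food rule does not match time since last meal or time of day between the Day 1 and Day 8 blood draws, which can add avoidable noise to the change in glucose and triglycerides

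*Protocol*

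**What the plan says.** The food rule appears in two sections of the protocol.

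- Section 8, Experimental Clinical Trial, covering the Day 1 and Day 8 assessments of all three groups: "Participants will be asked to arrive fasting or having not eaten for at least 2 hours before their visit".
- Section 14, on the first draw: "Participants will be asked to arrive having fasted for at least two hours, as a blood sample". On the second: "For this second collection, fasting for at least two hours will again be required".

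For timing, Section 8 says only that visit slots are arranged with the participant. It sets no clock window and does not tie the Day 8 slot to the Day 1 slot.

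The outcomes at issue are secondary endpoints of the clinical trial. Section 5 lists "high-density lipoprotein (HDL) levels, triglycerides, plasma glucose concentration, as well as biological markers from metabolomics, proteomics, and DNA methylation", and Section 8 compares "triglycerides, plasma glucose levels, also metabolomic, proteomic, and DNA methylation biomarkers before and after the 7-day intervention". The advanced omics work is conditional: "In a second phase, based on the initial results, advanced OMICs analysis will be conducted using high-resolution techniques". The methods named under Data Analysis and Evaluation are "multivariate logistic regression analysis, adjustment for confounding factors using mathematical modelling".

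**The concern.** Both draws share a minimum, but a minimum does not fix the state of the person who is sampled. Two hours without food and an overnight fast both satisfy the rule, and nothing asks that the same one apply at both visits. Plasma glucose and triglycerides depend on how recently a person has eaten, and so do many metabolites. If time since the last meal differs between Day 1 and Day 8, part of the measured change reflects the meal and not the seven days of walking, diet or usual routine.

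What is at stake is precision. The intervention is short and there are 60 participants per group, so extra within-person variation makes a real seven-day effect harder to see. A statistical analysis plan cannot restore a matched state once the blood is drawn. It can only adjust, and only if time since the last meal was recorded.

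The point concerns glucose and triglycerides, and metabolomics if that phase goes ahead. It is not made for waist circumference, blood pressure, HDL, proteomics or DNA methylation.

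**Working it through.** **Text check.** Sections 8 and 14 give the same minimum for both visits, with no upper limit, no requirement of equal duration and no time-of-day window. A participant with ten hours without food on Day 1 and two on Day 8 complies with both sections. The word *again* in Section 14 carries over the minimum, not the actual duration.

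**Figures in the plan.** There are none on this point. The protocol gives no SD for the change in any blood marker, and its sample-size calculation does not involve meal state. What follows is an illustration on assumed inputs.

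**Model.** Each person is in one of two states at each visit, fasted or non-fasted, and being non-fasted shifts the marker by s (in units of its between-person SD).

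- r: within-person correlation of the marker between visits, assumed 0.7.
- p: share non-fasted at each visit, assumed 0.5, 0.2 or 0.1.
- ρ: correlation of state between visits, first taken as 0 (independent).
- s: meal shift, assumed 0.2, 0.5 or 1.0 SD.

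The share of participants whose state differs between visits is d = 2p(1 − p)(1 − ρ).

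The variance of the raw change is 2(1 − r) + d·s². With r = 0.7 the first term is 0.60, so the relative increase is d·s²/0.60.

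| p | d (ρ = 0) | s = 0.2 | s = 0.5 | s = 1.0 |
|---|---|---|---|---|
| 0.5 | 0.50 | 0.020/0.60 = 3.3% | 0.125/0.60 = 20.8% | 0.50/0.60 = 83.3% |
| 0.2 | 0.32 | 0.0128/0.60 = 2.1% | 0.08/0.60 = 13.3% | 0.32/0.60 = 53.3% |
| 0.1 | 0.18 | 0.0072/0.60 = 1.2% | 0.045/0.60 = 7.5% | 0.18/0.60 = 30.0% |
| any, same state kept (ρ = 1) | 0 | 0% | 0% | 0% |

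Because p(1 − p) peaks at p = 0.5, the first row is the worst case for the non-fasted share.

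**If people tend to repeat their habits.** With ρ = 0.5 every increase halves: p = 0.5 gives 1.7, 10.4 and 41.7%, and p = 0.2 gives 1.1, 6.7 and 26.7%. With ρ = 0.9 and p = 0.5, d = 0.05 and the increases are 0.3, 2.1 and 8.3%.

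**With baseline adjustment.** Let v = 1 + p(1 − p)s² and c = r + ρp(1 − p)s². The residual variance v − c²/v is compared with 1 − r² = 0.51. For p = 0.5, ρ = 0 and s = 1.0: v = 1.25, c = 0.7, residual = 1.25 − 0.49/1.25 = 0.858, an increase of 68.2%. For s = 0.2 and 0.5 the increases are 2.9% and 17.9%. Adjusting for baseline lowers the penalty somewhat but does not remove it.

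**In terms of power.** Take an effect that would have 80% power at two-sided 0.05 with matched draws. If the variance rises by a fraction u, power is Φ((1.960 + 0.842)/√(1 + u) − 1.960). For u = 0.208 this is Φ(0.589), about 72%. For u = 0.833 it is Φ(0.109), about 54%. These figures only translate the assumed variance increases and add no evidence about their size.

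**The case against.** **The size is unknown.** The documents give no SD, no meal effect, no non-fasted share and no indication of how often people would change state. Both visits carry the same instruction, so many participants may arrive in the same state twice, and then the cost is nil or negligible. The plan names logistic regression, and inflation of a continuous change score does not carry over to it directly. All of this stands, and it limits the point to a possible loss of precision.

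**A reader might infer that Section 8 deliberately accepts two different states.** That reading is contestable. Section 14 uses the language of fasting for the two-hour rule itself, so the Section 8 wording may only restate one minimum. The point does not need the stronger reading, because a shared minimum without matching is enough.

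**A reader might also infer bias, especially in the Mediterranean-diet group,** where a Day 8 sample soon after eating could reflect the last meal. The documents do not support this. The rule is the same in all three randomised groups, nothing shows that meal timing would differ by group, and neither direction nor size can be derived.

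**The information may be collected anyway.** Hours since last meal and sampling time often sit on a visit form, which is not shown. The Section 18 data list does not mention them, but it is not exhaustive: its Day 1 and Day 8 list also omits waist circumference, which Section 8 measures. It therefore cannot be said that the analysis will be unable to adjust, only that the protocol text does not provide for it.

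**A longer fast is a burden.** This is fair. Participants are recruited for signs of metabolic disorder, and the Section 7 exclusions do not name diabetes. The remedy should not depend on a longer fast.

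**Conclusion.** The point holds as an optional, cheap improvement. The protocol sets a two-hour minimum for both draws and does not match time since last meal or time of day within a participant. This can add avoidable within-person noise to the change in glucose and triglycerides, and in metabolomics if the second phase proceeds.

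Under the stated assumptions (raw change, r = 0.7, independent state), the added variance runs from about 1% to 83%, with the upper end requiring half non-fasted and a full 1.0 SD meal shift. It is zero if each person keeps the same state. The range rests on a two-state simplification and assumed inputs, it does not model the named logistic regression, and it does not quantify time of day. The upper end should not be quoted as an expected loss. No bias is shown.

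**What to change.** In Sections 8 and 14, ask each participant to attend both visits in the same fasting state and at a similar time of day. The investigators choose the fasting length and should state it in the same terms in both sections. Record hours since last meal and sampling time at both draws, if the visit form does not already do so, so that the analysis can adjust for them.

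The cost is a sentence in the visit instructions, at most two form fields, and tighter scheduling of up to 180 × 2 = 360 visits, since the Day 8 slot has to follow the Day 1 slot. A longer fast, if chosen, adds participant burden. Keeping the two-hour minimum while matching and recording avoids that burden and still meets most of the concern.
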